4.3. Reporting

4.3.1. *Reporting of AEs and ADEs*

Information about all adverse events, whether volunteered by the patient, discovered by investigator questioning, or detected through physical examination, laboratory test or other means, will be collected and recorded on the Adverse Event e-CRF and followed as appropriate.

For the purpose of this study we will selectively collect AEs; meaning that only AEs directly or indirectly related to the EP intervention and/or any cardiac arrhythmia will be collected. Selective AE reporting is in line with the FDA's approach to a safety assessment that is focused on information that is useful and adds to current knowledge.

As far as possible, each adverse event will also be described by:

- its duration (start and end dates)
- the severity
- its relationship to the study device (unrelated/possible/probable)
- the action(s) taken

4.3.2. *Reporting of SAEs SADEs and USADEs*

For the purpose of this study and based on the definitions above and the requirements of the European authorities the following events are considered reportable events in accordance with Annex 7, section 2.3.5 and 93/42/EEC respectively:

- Any SAE whether or not considered as related to study device
- Any KODEX-EPD system deficiency that might have led to a SAE if:
 - a. Suitable action had not been taken, or
 - b. Intervention had not been made, or
 - c. If circumstances had been less fortunate
- New findings /updates in relation to already reported events

All USADEs, SAEs and SADEs, will be reported on specific forms, if applicable, and forwarded to the Sponsor within 24 hours of first awareness of the event. The Investigator is also responsible for complying with the applicable local requirements related to adverse event reporting.

The investigator must complete the appropriate event report form in English, assess the relationship to study device/procedure and e-mail the completed form to the Sponsor at:

[contact].

Follow-up information about previously reported USADEs, SAEs and SADEs must also be reported to the Sponsor within 24-hours of receipt. The Follow up information should be reported on a new event report form by referring to the subject and event number. Only new/updated information needs to be entered on the event report form.

Original and the duplicate copies of the event report forms must be kept at the study site. The monitor will review and collect copies of the completed event report forms and related documentation.

If the SAE has not been previously documented (new occurrence) and it is thought to be related to study device, Sponsor's Medical Expert may contact the investigator to obtain further information. If warranted, an investigator alert may be issued, to inform all investigators involved in any study with the same device that this serious adverse event has been reported.

5. STATISTICAL CONSIDERATION

5.1. Study Endpoints

5.1.1. *Primary Endpoints*

1. The accuracy, sensitivity, specificity and positive and negative predictive values of the KODEX-EPD PV occlusion feature as compared to conventional venographic method of fluoroscopy with contrast dye that will be used to guide the procedure.
2. The success of the freeze when freeze is initiated based on the assessment of the KODEX-EPD PV occlusion feature as compared to the success of the freeze when freeze is initiated based on the assessment with fluoroscopy and contrast dye.

5.1.2. *Secondary Endpoints*

- KODEX-EPD data collection
- Fluoroscopy system data collection
- Fluoroscopy time
- Fluoroscopy dose
- Number of contrast dye injections
- Contrast dye volume
- Time to isolation (TTI)
- Number of ablations per vein
- Procedure time (skin to skin)

5.2. Analysis Sets

The Primary Analysis Set (PAS) includes all successful occlusion tests. Successful is defined as a test for which;

- procedural data e.g.: KOPDEX-EPD system data, venograms, and notes are obtained.
- Presence of DTS, DTM or DTO notifications were documented before obtaining the shadow.

This analysis set will be used for the primary endpoint analysis.

The Secondary Analysis Set (SAS) includes all PVIs and ablations done. This analysis set will be used for the analysis of the secondary endpoints.

The ITT (intend to treat) PVs will be used as a secondary analysis of the secondary endpoints.

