2.2. Study Design

2.2.1. Study Schematic

[figure not shown]

Figure 3; Study Schematic

The Cryoballoon procedure consists of the isolation and ablation of the pulmonary veins (PVs). The number of PVs and occlusion tests per PV depends on several factors including patient anatomy. Therefore, data from the KODEX-EPD PV Occlusion feature will be evaluated as a separate set of data for each occlusion test and for each pulmonary vein. Data from a PVI where the diameter of the (common) PV ostium > 28mm, or when the threshold for Distance to Shadow (DTS), Distance to Mesh (DTM) or Distance to Ostium (DTO) is exceeded, or when the Achieve catheter is moving during the

injection, there is a double injection or an incorrect timing of the injection, will not be included in the primary endpoint analysis.

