2.6.2. Intervention

Patient management and treatment decisions are at the discretion of the care team per routine clinical practice. The KODEX-EPD system is an open-platform system however all catheters/leads used during the intervention need to be calibrated prior to the intervention.

2.6.2.1.Clinical Workflow

- 1) Advance the Achieve spiral mapping catheter (Achieve) to the Left Atrium (LA).
- 2) Image the LA with the Achieve by maneuvering the catheter around the LA under different angles.
- 3) Inflate the Cryoballoon (CB) and advance CB to occlude the ostium, make sure the location of the Achieve is maximal 15 mm distal to the CB. Hold this location for 5 seconds.
 - KODEX-EPD System will obtain a "shadow" of the Achieve at the current location this will take approximately 2 seconds.

Please note that there are 2 types of notifications on the KODEX-EPD system that can be shown when obtaining the 'shadow';

- **DTM; When the distance between the Achieve and the Mesh is > 10mm**
- **DTO; When the distance between the Achieve and the Ostium is > 35mm**

It is recommended to reposition the catheter and acquire a new shadow

- 4) Verify occlusion on fluoroscopy (in the blinded arm) or KODEX(in the KODEX guided arm) by selective contrast injection while simultaneously stepping on the KODEX-EPD System's foot pedal/or the injection button in the KODEX-EPD system is pressed to start the occlusion

assessment with the KODEX-EPD System. The occlusion assessment will take approximately 12 seconds. After which the physician should decide to;

- Proceed with CB ablation and move to next PV
- Reposition CB and repeat step 4.

Please note that for a successful occlusion assessment on the KODEX-EPD system it is important that;

- ***The there is no DTM, DTO or DTS (When the distance between the Achieve and the Shadow is > 10mm) notification on the KODEX-EPD system***
- ***The injection on the KODEX-EPD system is synced with the actual injection***
- ***The Injection is done with one shot.***

If occlusion is not indicated when assessing occlusion in the KODEX guided arm it is recommended to reposition the CB and re-assess the occlusion with KODEX. In total 3 consecutive attempts should be made to obtain occlusion on KODEX.

It is recommended to use an auto-injector where 6cc is injected at 2.5ml/sec and the dye/saline ratio is between 50/50 to 100/0.

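### The notification criterion in section 5.2 is wrong as written and is not aligned with the section 2.2.1 exclusions, so membership of the Primary Analysis Set needs rewording

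*Combined protocol and SAP*

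**What the plan says.** Section 5.2 states: "The Primary Analysis Set (PAS) includes all successful occlusion tests". A test is successful if it meets two criteria. The first is that the procedural data exist, with KODEX data, venograms and notes given as examples. The second is "Presence of DTS, DTM or DTO notifications were documented before obtaining the shadow". The set serves the primary endpoint analysis. Section 5.1.1 lists two primary endpoints: the five accuracy measures against venography, and the comparison of freeze success.

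Section 2.2.1 sets exclusions from that same analysis. The sentence starts "Data from a PVI where the diameter of the (common) PV ostium > 28mm, or when the threshold for Distance to Shadow (DTS", goes on to DTM, DTO and movement of the Achieve catheter, and ends "there is a double injection or an incorrect timing of the injection, will not be included in the primary endpoint analysis". Just before it, the section says that the occlusion data "will be evaluated as a separate set of data for each occlusion test and for each pulmonary vein".

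Section 2.6.2.1 describes the notifications at two steps.
- At acquisition of the shadow: "Please note that there are 2 types of notifications on the KODEX-EPD system that can be shown when obtaining the 'shadow". The two are DTM (Achieve to mesh) and DTO (Achieve to ostium). The advice is then: "It is recommended to reposition the catheter and acquire a new shadow".
- At the occlusion assessment, one condition for success is that "there is no DTM, DTO or DTS (When the distance between the Achieve and the Shadow is > 10mm) notification" is on the system.

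**The concern.** An analysis-set definition should let two analysts who work separately arrive at the same list of tests. Here the section that defines the set asks for documented presence of a notification, while two other sections treat a notification as a reason against the test. Section 5.2 also places the check at a moment that does not fit the workflow. Neither 5.2 nor 2.2.1 refers to the other.

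At stake is what the accuracy, sensitivity, specificity and predictive values describe. Without flagged tests (those with a DTS, DTM or DTO notification) they describe the feature under clean acquisition. With flagged tests they describe it as it is used. No other analysis in the plan would show the difference, because the Secondary Analysis Set and the ITT set are reserved for the secondary endpoints.

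**Working it through.** The point rests on wording, so the check sets the sections side by side. No planned figure is in dispute.

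**1. Direction.**
- 5.2, literally: a notification must have been present.
- 5.2, as a documentation rule: notification status must have been recorded, so flagged and unflagged tests both qualify.
- 2.2.1: tests over a threshold are out.
- 2.6.2.1: a successful assessment has no notification.

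The literal reading reverses 2.2.1. The documentation reading agrees with 2.2.1 only if the exclusions are applied on top, and 5.2 does not say that they are.

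**2. Timing.** DTS is the distance between the Achieve and the shadow. For the shadow used in a test, its status cannot exist before that shadow does. DTM and DTO are shown while the shadow is being obtained. The workflow also allows the balloon to be repositioned and step 4 repeated, whereas the shadow is acquired in step 3. A repeat test may therefore rely on an existing shadow, and its DTS status then arises after the only moment that 5.2 names.

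**3. Completeness.** 5.2 lists none of the other 2.2.1 exclusions either: ostium above 28 mm, Achieve movement, double injection, mistimed injection. Its two criteria cannot be the whole definition.

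**4. Can flagged tests reach the data?** Yes. Repositioning after a DTM or DTO notification is recommended and not required.

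**5. Level of exclusion.** 2.2.1 speaks of data from a PVI, and 5.2 counts tests. Test level has the better support: 2.2.1 evaluates each test separately, and 5.4.2.1 summarises by occlusion test first. For the exclusions themselves it is not stated.

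**6. Size.** Let a be accuracy in unflagged tests, f the flagged share of tests with a KODEX result, and g the accuracy gap between unflagged and flagged tests.
- Accuracy with flagged tests in: (1 − f)·a + f·(a − g) = a − f·g.
- Shift between the two sets: f·g.

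The documents give neither f nor g. Under assumed values:
- f = 5%, g = 5 points: 0.05 × 5 = 0.25 points.
- f = 15%, g = 20 points: 0.15 × 20 = 3.0 points.
- f = 25%, g = 30 points: 0.25 × 30 = 7.5 points.

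Another choice with no better support takes 92.1% (the baseline-workflow figure in 1.3.1.1) for unflagged tests and 70% for flagged ones, so g = 22.1. With f from 10% to 40%, the shift is 0.10 × 22.1 = 2.2 to 0.40 × 22.1 = 8.8 points. The answer follows the assumption. If the system returns no result when a notification is shown, f = 0 and the shift is 0; only the count of non-evaluable tests changes.

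**The case against.** The strongest reply is that the intent is plain. Section 2.2.1 is unqualified, 2.6.2.1 agrees with it, and 5.2 uses the same word, successful, that 2.6.2.1 ties to the absence of notifications. Both 5.2 criteria can be read as documentation conditions, with an inclusion set and an express exclusion applying together. This largely stands and sets the limit of the point. What remains is that the criterion does not say this, and its timing clause cannot be followed for the shadow in use.

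Several stronger readings are tempting, and the documents do not support them.
- A reader might infer that only flagged tests enter the set. The words allow it, but 2.2.1 and 2.6.2.1 rule it out as intent.
- A reader might infer that 5.2 and 2.2.1 cannot be reconciled. They can, by the reading above.
- A reader might call the timing impossible in every case. A new shadow may be acquired, so a notification against a previous shadow can come before the one finally used. The impossibility holds only for DTS against the shadow used in that test.
- A reader might infer that the choice would go unreported. Keeping flagged tests departs from an express sentence in 2.2.1, so it is arguably a change that 5.5.2 requires to be documented.
- A reader might infer that the reported accuracy will be inflated by some number of points, or set a shift against the 90% criterion in 1.3.1.1. That criterion belongs to a retrospective validation, nothing says that its figures came from unflagged tests, and this study sets no such threshold.

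**Conclusion.** The point holds as a drafting error in a stated rule. The second criterion of 5.2 has the wrong direction if taken literally, has a timing clause that does not fit the workflow, and is not tied to the 2.2.1 exclusions that evidently should govern. The textual finding needs no assumption.

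Its numerical effect is not knowable from the documents and may be zero. The shifts shown in the working illustrate the formula and are not estimates. Section 5.4.1 plans descriptive analysis only, without inference, and there is no success threshold to cross. Severity is minor to should-fix: it deserves correction because it determines which tests enter a primary endpoint, and it does not threaten the study.

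**What to change.** 1. Keep the first criterion of 5.2, including the notes, because section 2.6.7.3 has the physician's visual occlusion reading documented there. Replace the second with: notification status (present or absent) for the test is documented, and none of the 2.2.1 exclusions applies. State how the set applies to each of the two primary endpoints, with endpoint 1 using blinded-arm tests, the arm on which 5.3 sizes it.
2. Delete the timing clause (the last four words of the criterion). Tie notification status to the shadow used for that test and to the occlusion assessment, as 2.6.2.1 does.
3. State in 2.2.1 that notifications, Achieve movement and a double or mistimed injection remove the single test, and that an ostium above 28 mm removes the vein.
4. Report the number of tests excluded for each reason. Add one descriptive sensitivity analysis of endpoint 1 that keeps flagged tests with a KODEX result.

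The cost is a few sentences, one table and one extra analysis. The sponsor should also confirm that the exclusion reasons are captured. The data lists in 2.6.2.2 and Table 1 do not name notification status, ostium diameter, Achieve movement or injection timing, although the stored KODEX data and cineloops may hold some of them. The downside is that accuracy over all tests may look less favourable. None of this changes how patients are treated.

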
STUDY VISIT SCHEDULE AND PROCEDURES
	
This is an acute study with no follow-up.
 
Before the procedure (Baseline):
 
 1. Eligibility according to inclusion and exclusion criteria 2. Obtaining signed Informed Consent Form (ICF) 3. Demographics 4. Medical history 5. Physical examinations 6. Concomitant medications 7. Presence/history of atrial fibrillation 8. Previous and current treatments of atrial fibrillation 
During procedure:
 
 1. Delivery of standard therapy. The study device will be used in the cryoballoon ablation procedure according to the instructions for use. PV occlusion will be assessed with the KODEX-EPD PV occlusion feature. 
 - Blinded Arm; The physician will be blinded for the KODEX-EPD occlusion data and use conventional venographic method of fluoroscopy with contrast dye to guide the procedure. - KODEX guided Arm; the physician will use the KODEX-EPD occlusion data to guide the procedure 2. Confirmation of therapy. Confirm PV isolation using standard practice. 3. Adverse events Reporting.

PRIMARY ENDPOINTS
	
 1. The accuracy, sensitivity, specificity and positive and negative predictive values of the KODEX-EPD PV occlusion feature as compared to conventional venographic method of fluoroscopy with contrast dye that will be used to guide the procedure. 2. The success of the freeze when freeze is initiated based on the assessment of the KODEX-EPD PV occlusion feature as compared to the success of the freeze when freeze is

	initiated based on the assessment with fluoroscopy and contrast dye.
SECONDARY/ EXPLORATORY ENDPOINTS	
Procedure data collection:
 
• KODEX-EPD data collection• Fluoroscopy system data collection• Fluoroscopy time• Fluoroscopy dose• Number of contrast dye injections• Contrast dye volume• Information on durability of the PV isolation.• Time to isolation (TTI)/Success of Isolation• Number of ablations per vein• Procedure time (skin to skin)
SPONSOR	EPD Solutions is the sole study sponsor. This study will be conducted according to US 21 CFR 11, 50, 54, 56, 812, ISO 14155: 2020, the ICH Guidelines for GCP, the Declaration of Helsinki (2013) and all other applicable local and national regulations. The study will be registered on www.clinicaltrials.gov .

Acronyms and Definitions

AE	Adverse Event
CRF	Case Report Form

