Current clinical studies on the KODEX-EPD occlusion feature have reported on the safe and effective use of the system in standard practice. However, the performance of the KODEX-EPD occlusion feature has not been evaluated using a standardized workflow in a blinded setting in a homogenous patient group. Furthermore, in an effort to minimize therapy, a direct comparison between the success of the freeze when initiating therapy based on the occlusion feature vs the assessment of occlusion by fluoroscopy has not been evaluated. The study design indicates a post-market interventional clinical

investigation to evaluate the endpoints of the study. No follow-up is foreseen ensuring a minimal burden to the subjects participating in the study.

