2.2.3. Secondary and Exploratory Endpoints

Procedure data collection:

- KODEX-EPD data collection
- Fluoroscopy system data collection
- Fluoroscopy time
- Fluoroscopy dose
- Number of contrast dye injections
- Contrast dye volume
- Time to isolation (TTI)/Success of Isolation
- Number of ablations per vein
- Procedure time (skin to skin)

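### As written, primary endpoint 2 (freeze success) is filtered on KODEX acquisition quality in both arms, no by-arm result over all treated veins is planned, and sections 2.2.1 and 5.2 are not reconciled

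*Combined protocol and SAP*

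**What the plan says.** **Endpoint 2.** Section 5.1.1 names as second primary endpoint "The success of the freeze when freeze is initiated based on the assessment of the KODEX-EPD PV occlusion feature", set against freeze success when fluoroscopy with contrast was the basis. Section 1.3.3 gives the motive: what has not yet been evaluated is "a direct comparison between the success of the freeze when initiating therapy based on the occlusion feature vs the assessment of occlusion by fluoroscopy".

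**Guidance in the blinded arm.** The Study Synopsis says: "The physician will be blinded for the KODEX-EPD occlusion data and use conventional venographic method of fluoroscopy with contrast dye to guide the procedure".

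**Analysis sets (5.2).** The PAS consists of successful occlusion tests. A test is successful if the procedural data (KODEX data, venograms, notes) were obtained and if "Presence of DTS, DTM or DTO notifications were documented before obtaining the shadow". Then: "This analysis set will be used for the primary endpoint analysis". For the other sets: "The Secondary Analysis Set (SAS) includes all PVIs and ablations done", for use with the secondary endpoints, and "The ITT (intend to treat) PVs will be used as a secondary analysis of the secondary endpoints". The ITT PVs are not defined.

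**Exclusions (2.2.1).** Data are left out of the primary endpoint analysis when the ostium exceeds 28 mm, a DTS, DTM or DTO threshold is exceeded, the Achieve catheter moves during injection, the injection is double, or its timing is wrong. The section does not limit this to endpoint 1.

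**Summaries.** Section 5.4.2.1 summarises primary results by test, vein and patient, and 5.4.2.2 summarises secondary results by vein and patient. Neither mentions arm.

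**The concern.** The two primary endpoints ask different things. Endpoint 1 is diagnostic accuracy, and an occlusion test that KODEX could not read properly cannot sensibly be scored. Endpoint 2 compares the result of freezes started under two guidance methods. There, a filter on KODEX acquisition means something different in each arm. In the guided arm, poor acquisition is part of how the guidance performs in use. In the blinded arm, it is a property of a system whose output the operator did not see.

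If the filter applies to endpoint 2, the reader gets freeze success only where KODEX acquisition was adequate, with no planned by-arm freeze result over all treated veins beside it. Separately, because 5.2 and 2.2.1 state different rules without referring to each other, two analysts could build different denominators for both primary endpoints.

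**Working it through.** **1. The plan's own figure.** Section 5.3 sizes endpoint 2 at 87, from an expected 80% and a lower 95% limit of about 70%. The exact (Clopper-Pearson) lower limit with 0.025 in the lower tail, at 80% of 87, is 0.7005, so 87 reproduces. 87 / 4 = 21.75, which matches the stated 22 subjects at an implied four units each. The one-sided label is a separate matter. The figure does not tell us what share of tests or veins will be excluded, and no figure in the plan is wrong because of this point.

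**2. Where the conditioning comes from.** Section 5.2 alone requires that data exist and that flags be documented, so a flagged test can qualify. Section 2.2.1 is what removes flagged data. Apart from ostium diameter, which is anatomical, its reasons concern catheter position, catheter movement or the injection. Section 2.6.2.1 gives absence of DTM, DTO and DTS flags, a synchronised injection and a single shot as conditions for a successful KODEX assessment. These reasons are therefore about KODEX acquisition.

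**3. Whether it reaches endpoint 2.** Section 2.2.1 excludes from the primary endpoint analysis, and 5.2 assigns one set to that analysis. Section 5.1.1 lists two primary endpoints. Neither section makes an exception for endpoint 2. Taken as written, the filter applies to both endpoints and both arms.

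**4. Whether another planned result fills the gap.**
- The all-vein set (SAS) and the ITT PVs serve secondary endpoints only.
- Freeze success is not a secondary endpoint.
- Section 2.2.3 lists "Time to isolation (TTI)/Success of Isolation", but 5.1.2 keeps only TTI, and isolation success is nowhere equated with freeze success.
- The number of ablations per vein is in 5.1.2 and would be summarised on the SAS. It is related and covers every vein, but it is not freeze success.

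**5. The two rules side by side.**
- *Flagged test, flag documented:* admitted by 5.2 read alone, excluded by 2.2.1.
- *Timing:* 5.2 wants DTS documented ahead of shadow acquisition. Section 2.6.2.1 defines DTS as the distance between the Achieve and the shadow, with a 10 mm threshold. For a first shadow there is nothing yet to measure from. Only when an earlier shadow exists could the rule be met.
- *Unit:* 2.2.1 speaks of data from a PVI, while a double or mistimed injection belongs to one test, and 2.6.2.1 allows repeat tests of the same vein. Removing the test and removing the vein give different denominators.

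**6. Direction and size.** In each arm let d be the share of veins lost, r the success in retained veins and s the success in lost veins. The all-vein rate is (1 − d)r + ds, so the retained-vein rate departs from it by r − [(1 − d)r + ds] = d(r − s). The between-arm difference departs by dG(rG − sG) − dB(rB − sB), with G for guided and B for blinded. The documents give no d or s for either arm. The only success figure is the expected 80% used to size the guided arm, with no statement of whether it means retained or all veins. Neither sign nor size can be determined, and the departure is zero if d(r − s) is equal in the two arms.

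**The case against.** **The conditioning is largely the endpoint itself.** Endpoint 2 is worded as success when the freeze was started on the KODEX assessment, so veins frozen without it fall outside. This stands for the guided arm, and it is why endpoint 2 should stay on the PAS. It does not explain filtering the blinded arm on KODEX quality.

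**Section 2.2.1 may be aimed at endpoint 1.** Its exclusions follow a sentence about evaluating the KODEX occlusion data. That reading is possible, but the text refers to the primary endpoint analysis as a whole. At the least, the scope must be stated.

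**The two sections can be read cumulatively:** document the flag, then exclude. That is a fair reading, and a reader who infers an outright contradiction goes too far. The conflict arises only if each is read alone, but neither refers to the other, and the DTS timing is faulty on any reading.

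**The unit is natural.** Ostium size belongs to the vein and most other reasons to the test. This is sensible but not stated.

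**The study is descriptive and non-randomised, and the guided arm is at one centre.** True, and an all-vein table would not remove that confounding. A descriptive percentage still needs a defined denominator.

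**Whole-vein loss may be small.** Section 2.6.2.1 recommends repositioning and a new shadow after a DTM or DTO flag. A flagged test replaced by a later clean one costs no vein. This is a good reason not to assume a large effect.

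That the summaries do not name arm carries little weight alone, since the endpoint's wording implies the comparison.

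**Conclusion.** The point holds as a mismatch between analysis set and endpoint, together with an unreconciled inclusion rule. It should be settled before analysis. It rests on taking 2.2.1 at its word as covering both primary endpoints.

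No size can be put on it. A reader might infer that the plan inflates guided-arm success or favours KODEX. The documents do not support that: both arms are filtered, and neither the shares excluded nor the success in excluded veins is given. Nor should a reader infer that no all-vein information is planned, since the number of ablations per vein gives some. Nor does it follow that endpoint 2 is on the wrong set altogether, because its wording is conditional on the KODEX assessment.

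The undefined ITT PVs and the absence of isolation success from 5.1.2 are minor clarifications and do not carry the finding. The lack of a definition of freeze success is a separate gap, relevant here because any added table needs one.

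**What to change.** 1. **One PAS rule.** Reconcile 2.2.1 and 5.2 into a single rule. It should say whether flagged tests are excluded, whether the unit is the test or the vein for each reason, whether the rule applies to endpoint 2, and when DTS status is recorded, at a time when it can exist.
2. **One supplementary descriptive table.** Keep endpoint 2 on the PAS as worded. Add freeze success per vein by arm over all treated veins (SAS), with guided-arm veins kept in their arm whatever the KODEX assessment showed. Use one stated definition of freeze success built on the cryoconsole and isolation data already collected.
3. **Exclusion counts.** Tabulate excluded tests and veins by arm and reason, as far as recorded.
4. **Minor.** Define the ITT PVs or delete the term, and restore isolation success to 5.1.2.

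The cost is wording in 2.2.1, 5.1.2, 5.2 and 5.4.2.1, one definition, and one or two tables. Cryoconsole freeze data are already collected under 2.6.2.2, but TTI only where possible. Ostium diameter and Achieve movement are not named among the collected items, so the table of reasons may be incomplete unless the KODEX data or notes hold them. The downside is one more descriptive result to explain in a non-randomised study, and a possibly lower guided-arm percentage.
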